6.1. Inclusion Criteria

Patients are eligible for inclusion in the study only if they meet all of the following criteria at screening:

Type of Patient – Patient and Disease Characteristics

[1] Males or females (of non-childbearing potential) \geq 50 years of age

Note: Females of non-childbearing potential are defined as women ≥60 years of age, postmenopausal women ≥50 and <60 years of age who have had a cessation of menses for at least 12 months, or women who are congenitally or surgically sterile (i.e., have had a hysterectomy or bilateral oophorectomy or tubal ligation).

To confirm postmenopausal status for women ≥50 and <60 years of age who have had a cessation of menses for at least 12 months, follicle stimulating hormone levels will be assessed and must be ≥40 mIU/mL.

Note: Males must agree to use 2 forms of highly effective birth control (see below) with female partners of childbearing potential while enrolled in the study, and for at least 28 days following the last dose of investigational product.

The following birth control methods are considered highly effective:

- Oral, injectable, or implanted hormonal contraceptives
- Condom with a spermicidal foam, gel, film, cream, or suppository
- Occlusive cap (diaphragm or cervical/vault caps) with a spermicidal foam, gel, film, cream, or suppository
- Intrauterine device
- Intrauterine system (e.g., progestin-releasing coil)
- Vasectomized male (with appropriate postvasectomy documentation of the absence of sperm in the ejaculate).
- [2] Ambulatory (with or without walking device) with a stable gait as assessed with a TUG test (Okumiya et al. 1998; Nordin et al. 2006) that must be completed in

- \leq 30 seconds. The test may be repeated once with instruction. Patients in wheelchairs are also eligible and do not need to complete the TUG test.
- [3] Have an MMSE score of 10 to 24.
- [4] Meets clinical criteria for one of the following disorders: dementia associated with Parkinson's disease, dementia with Lewy bodies, possible or probable Alzheimer's disease, frontotemporal degeneration spectrum disorders, vascular dementia.
- [5] Must be able to communicate verbally.
- [6] At Visit 1 (screening) and Visit 2 (Week 0) have at least ONE of the following:
 - o an NPI score of ≥ 4 on either delusions or hallucinations individual items
 - o an NPI score of ≥6 on the Psychosis Subscale (combined delusions and hallucinations)
 - o an NPI score of ≥4 on agitation/aggression domain
- [7] Have a reliable caregiver to accompany the patient to all study visits. This caregiver must provide written informed consent to participate and be in frequent contact with the patient (defined as spending at least 4 hours/day at least 4 days/week with the patient and who is knowledgeable about the patient's daytime and nighttime behaviors). The caregiver must be able to communicate with site personnel, and in the opinion of the investigator, must understand the written protocol-specified questionnaires. If a caregiver cannot continue, one replacement caregiver will be allowed if the above criterion is met.
- [8] Must be on a stable dose of cholinesterase inhibitor and/or memantine, if applicable.
- [9] If taking antipsychotic drugs or any drug intended to treat psychosis, must be on a stable treatment regimen for ≥1 month prior to the baseline visit (Visit 2). Note: If the patient has recently stopped taking antipsychotic drugs or any drug intended to treat psychosis, he or she must have discontinued treatment at least 4 weeks before Visit 1 (screening).
- [10] Have venous access sufficient to allow for blood sampling per the protocol.
- [11] Have clinical laboratory test results within normal reference range for the population or investigative site, or results with acceptable deviations that are judged to be not clinically significant by the investigator.
- [12] Are capable of participating in all study assessments in the opinion of the investigator.

Informed Consent

[13] Are able and willing to provide consent (patients and caregivers).

6.2. Exclusion Criteria

Patients will be excluded from participating in the study if they meet any of the following criteria:

Diagnostic Assessments

- [14] Have a history of significant psychotic disorders (including, schizophrenia, delusional disorder, substance abuse psychosis that lasted over 6 months, major depressive disorder or bipolar disorder with psychotic episodes).
- [15] Has a history of ischemic stroke within the last 12 months or any evidence of hemorrhagic stroke.

Medical Conditions

- [16] Have renal impairment as defined by eGFR <45 ml/min/1.73m² using the Chronic Kidney Disease Epidemiology Collaboration Cystatin C Equation (Grubb et al. 2010; Peralta et al. 2011; Inker et al. 2012).
- [17] Have significant cardiovascular, respiratory, gastrointestinal, renal, hematologic, or oncologic comorbidities that could impact patient safety and study participation over 10 weeks.
- [18] Have a history of seizures (other than remote history of childhood febrile seizure) or other condition that would place the patient at increased risk of seizures. Patients taking anticonvulsants for seizure control are also excluded.
- [19] Are, in the investigator's judgment, at risk for suicide, including patients who have answered 'yes' to either Question 4 (Active Suicidal Ideation with Some Intent to Act, Without Specific Plan) or Question 5 (Active Suicidal Ideation with Specific Plan and Intent) on the Suicidal Ideation portion of the Columbia Suicide Severity Rating Scale (C-SSRS), or answered 'yes' to any of the suicide-related behaviors (actual attempt, interrupted attempt, aborted attempt, preparatory act or behavior) on the Suicidal Behavior portion of the C-SSRS; and the ideation or behavior occurred within a month of Visit 1 (screening).
- [20] Have a Fridericia's corrected QT interval (QTcF) >450 ms (males) or 470 ms (females) at Visit 1 (screening).

Prior/Concurrent Clinical Trial Experience

- [21] Are currently enrolled in any other clinical trial involving an investigational product or any other type of medical research judged not to be scientifically or medically compatible with this study.
- [22] Have participated, within the last 30 days, in a clinical trial involving an investigational product. If the previous investigational product has a long half-life, 3 months or 5 half-lives (whichever is longer) must have passed.

Other Exclusions

- [23] Are investigator site personnel directly affiliated with this study and/or their immediate families. Immediate family is defined as a spouse, parent, child, step-child or sibling, whether biological or legally adopted.
- [24] Are Mediti Pharma, Inc. or Eli Lilly and Company employees or immediate family members of employees; or are employees of any third-party involved in the study who require exclusion of their employees. This pertains to both caregivers and patients.
- [25] In the opinion of the investigator or sponsor, are unsuitable for inclusion in the study.

6.3. Lifestyle and/or Dietary Requirements

Throughout the study, patients may undergo medical assessments and review of compliance with requirements before continuing in the study.

Study participants should be instructed not to donate blood or blood products during the study or for 8 weeks following the study.

6.4. Screen Failures

Individuals who do not meet the criteria for participation in this study (screen failure) may be re-screened 1 time with sponsor approval. The time period from screen fail to rescreen will be determined by the investigator. If rescreening is performed, a new informed consent form (ICF) must be signed, and the patient will be assigned a new identification number. Additionally, all screening procedures must be conducted at rescreen to ensure all eligibility criteria are met.

At screening and throughout the study, procedure/lab retests may be conducted at the discretion of the investigator and do not constitute a rescreen.

7. Treatment

7.1. Treatment Administration

This study compares 60-mg MP-101 versus matching placebo administered orally QD for 10 weeks. Table 7.1 shows the treatment regimens.

Three capsules of 20-mg MP-101 and/or placebo will be ingested with 240 mL of room temperature water with the patient in an upright position. Doses should be administered at approximately the same time in the morning each day. For all visits that include PK sampling, the approximate start and stop times of food consumption prior to dosing and up to 4 hours postdose will be recorded as detailed in Section 9.5.1.

Table 7.1. Treatment Regimens

		Dose	
Treatment Arm	Week 0	Week 1	Week 2 through Week 9
MP-101	20-mg MP-101 QD	40-mg MP-101 QD	60-mg MP-101 QDa
	$(1 \times 20$ -mg caps and	$(2 \times 20$ -mg caps and	$(3 \times 20$ -mg caps)
	2 placebo caps)	1 placebo cap)	
Placebo	Placebo QD	Placebo QD	Placebo QD
	(3 placebo caps)	(3 placebo caps)	(3 placebo caps)

Abbreviations: caps = capsule; QD = once daily; TEAE= treatment-emergent adverse event.

The investigator or designee is responsible for:

- explanation of the correct use of the investigational product(s) to the patient/caregiver/site personnel,
- verification that instructions are followed properly,
- maintenance of accurate records of investigational product receipt, dispensing and collection, and
- return of all unused and used medication to Mediti Pharma, Inc. or its designee at the end of the study.

Note: In some cases, sites may destroy the material if, during the investigative site selection, the evaluator has verified and documented that the site has appropriate facilities and written procedures to dispose of clinical trial materials.

7.1.1. Packaging and Labeling

The specific dose strength of the drug product (DP), MP-101 DP, corresponds to the free acid equivalent (i.e., 20-mg MP-101 DP is equivalent to 20-mg LY2979165 free acid equivalent).

MP-101 will be provided in a wallet design (blister pack) containing blister strips. Each wallet will contain 9 rows of 3 capsules each. Placebo capsules that look identical to MP-101 capsules, but contain no active ingredient, will also be provided.

a Refer to Figure 7.1 for the dose titration schedule.

Clinical trial materials will be labeled according to the country's regulatory requirements.

7.2. Method of Treatment Assignment

Patients who meet all criteria for enrollment will be randomized in a 1:1 ratio (MP-101:placebo) to double-blind treatment at Visit 2 (Week 0). Assignment to treatment arms will be determined by a computer-generated random sequence using an interactive web-response system (IWRS). The IWRS will be used to assign blister packs containing double-blind investigational product to each patient. Blister packs will be dispensed at Visits 2, 4, 5, and 6, (Weeks 0, 2, 4, and 6, respectively). During the patient's visit, the site will access the IWRS for the correct blister pack numbers to dispense.

Randomization will be stratified by baseline MMSE score and eGFR value:

- MMSE < 16 or MMSE > 16
- eGFR <60 or eGFR > 60

7.2.1. Timing of Dose Administration

The dose will be administered at approximately the same time in the morning each day. Patients will record the actual time of each dose of study drug and the time of food consumption before and after each dose; this information will be collected.

7.3. Blinding

Blinding will be maintained throughout the conduct of the trial until all data are verified to an acceptable level of quality and locked.

Select individuals may gain access to unblinded data prior to the final database lock to initiate the final population PK model development. The individuals and unblinded data will be specified in the unblinding plan section of the Statistical Analysis Plan (SAP) or a separate unblinding plan document.

If, in the opinion of the investigator or the Mediti Pharma, Inc. clinical research physician (CRP) or designee, unblinding of patients is necessary for the management of adverse or other clinically relevant events, the patients' treatment code will be made available.

Emergency unblinding for AEs may be performed through the IWRS, which may supplement or take the place of emergency codes generated by a computer drug-labeling system. This option may be used ONLY if the patient's well-being requires knowledge of the patient's treatment assignment. All unblinding events are recorded and reported by the IWRS.

If an investigator, site personnel performing assessments, or patient is unblinded, the patient must be discontinued from the study. In cases where there are ethical reasons to have the patient remain in the study, the investigator must obtain specific approval from a Mediti Pharma, Inc. or designated CRP for the patient to continue in the study.

In case of an emergency, the investigator has the sole responsibility for determining if unblinding of a patient's treatment assignment is warranted. Patient safety is the primary consideration in

making such a determination. If the investigator decides that unblinding is warranted, the investigator should make every effort to contact the Mediti Pharma, Inc. CRP prior to unblinding, unless a delay compromises patient safety. If a patient's treatment assignment is unblinded, Mediti Pharma, Inc. must be notified immediately.

Upon completion of the study, all codes must be returned to Mediti Pharma, Inc. or its designee.

7.4. Dose Titration

Figure 7.1 illustrates the dose titration schedule.

[figure not shown]

Figure 7.1. Dose titration schedule for protocol MP-101-01.

At Visit 2 (Week 0), patients will be randomized to the MP-101 arm or the placebo arm. All patients will start at a dose of 20 mg or equivalent placebo (Figure 7.1). If intolerance is reported at a dose of 20 mg between Visit 2 (Week 0) and Visit 3 (Week 1), the patient will be discontinued from the study. Intolerance is defined as the inability to tolerate TEAEs such as dizziness, nausea, and vomiting, which in the opinion of the investigator are possibly related to MP-101.

At Visit 3 (Week 1), the dose of MP-101 (or equivalent placebo) will be increased to 40 mg. If intolerance is reported at a dose of 40 mg between Visit 3 (Week 1) and Visit 4 (Week 2), the patient will be discontinued from the study.

At Visit 4 (Week 2), the dose of MP-101 (or equivalent placebo) will be increased to 60 mg. If intolerance is reported at a dose of 60 mg between Visits 4 (Week 2) and 5 (Week 4), the patient will be asked to return for an unscheduled visit for down-titration to 40 mg. Patients down-titrated to 40 mg prior to Visit 5 (Week 4) will remain at this dose for the remainder of the study.

At Visit 5 (Week 4), the dose of MP-101 (or equivalent placebo) will be maintained at 60 mg. If intolerance is reported at a dose of 60 mg at Visit 5 (Week 4), the patient will be down-titrated to 40 mg and will remain at this dose for the remainder of the study. If intolerance is reported at a dose of either 40 mg or 60 mg beyond Visit 5 (Week 4), the subject will be discontinued from the study.

7.5. Preparation/Handling/Storage/Accountability

Only participants enrolled in the study or their designated caregivers may receive investigational product and only authorized site staff may supply study treatment. All study treatments should be stored in an environmentally controlled and monitored (manual or automated) area in accordance with the labeled storage conditions with access limited to the investigator and authorized site staff.

The investigator, institution, or head of the medical institution (where applicable) is responsible for study treatment accountability, reconciliation, and record maintenance (such as receipt, reconciliation and final disposition records). A Mediti Pharma, Inc. delegate (e.g., site monitor) will conduct an accountability assessment.

7.6. Treatment Compliance

Patient compliance with investigational product will be assessed at each visit. Compliance will be assessed by direct questioning and documentation of returned capsules. Patient compliance with study drug will also be recorded in the patient diary.

Patients who are noncompliant will be discontinued from the study. A patient will be considered noncompliant if he or she misses more than 5 consecutive days of investigational product at 60 mg, or more than 10 cumulative days of investigational product at 60 mg during the study. Similarly, a patient will be considered noncompliant if he or she is judged by the investigator to have intentionally or repeatedly taken more than the prescribed amount of medication.

7.7. Concomitant Therapy

Patients on stable concomitant medication at the time of study entry (e.g., AChEIs) should continue their regular, unchanged dose throughout the study. Any medication used during the course of the study must be documented. A list of Excluded Concomitant Medications is presented in Table 7.2. Questions concerning the excluded medications should be directed to the sponsor. Use of any of the listed medications would result in either a screen fail (see Section 6.2) or discontinuation from the study.

Patients with worsening psychosis or agitation/aggression requiring rescue therapy will be withdrawn from the study.

Table 7.2. List of Excluded Concomitant Medications

rug Class	
pioids, tramadol, ketorolac except occasional use as needed	
ntiemetics (except occasional use as needed metoclopramide, domperidone, other dopamine rec	ceptor
ockers)	
ntihistamines (except occasional use as needed)	
ydroxyzine (except occasional use as needed)	
ypnotics	
thium	
sychostimulants (modafanil)	
celetal muscle relaxants (except occasional use as needed)	

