8.1. Discontinuation from Study Treatment

8.1.1. Permanent Discontinuation from Study Treatment

Discontinuation of dosing for abnormal liver tests should be considered by the investigator when a patient meets 1 of the following conditions, after consultation with the Sponsor designated medical monitor:

- alanine aminotransferase (ALT) or aspartate aminotransferase (AST) >8 × upper limit of normal (ULN)
- alanine aminotransferase or AST >5 × ULN for more than 2 weeks
- alanine aminotransferase or AST >3 \times ULN and total bilirubin level (TBL) >2 \times ULN or prothrombin time >1.5 \times ULN
- alanine aminotransferase or AST >3 × ULN with the appearance of fatigue, nausea, vomiting, right upper-quadrant pain or tenderness, fever, rash, and/or eosinophilia (>5%)
- alkaline phosphatase (ALP) >3 × ULN
- alkaline phosphatase $>2.5 \times ULN$ and TBL $>2 \times ULN$
- alkaline phosphatase >2.5 × ULN with the appearance of fatigue, nausea, vomiting, right-quadrant pain or tenderness, fever, rash, and/or eosinophilia (>5%)

In addition, patients will be discontinued from the investigational product in the following circumstances:

- the occurrence of worsening psychosis and/or agitation or aggression requiring rescue therapy
- the occurrence of an SAE that in the opinion of the investigator would preclude the patient from continuing in the study
- the occurrence of a clinically significant event, which is defined as a moderate (Grade 2) AE, laboratory result, ECG finding, or vital sign change based on the Common Terminology Criteria for Adverse Events v4.03 (CTCAE) or most current version, that in the opinion of the investigator would preclude the patient from continuing in the study. Clinically significant events of special interest include vomiting or "dizziness" associated with balance and gait instability as assessed for ambulatory patients using the TUG test

For patients who discontinue the investigational product early, sites will make every reasonable effort to ensure that patients have procedures performed as shown in the Schedule of Activities (Section 2).

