8.2. Discontinuation from the Study

Patients may be discontinued in the following circumstances:

- enrollment in any other clinical trial involving an investigational product or enrollment in any other type of medical research judged not to be scientifically or medically compatible with this study
- participation in the study needs to be stopped for medical, safety, regulatory, or other reasons consistent with applicable laws, regulations, and good clinical practice (GCP)
- investigator decision
 - o the investigator decides that the patient should be discontinued from the study
 - o if the patient, for any reason, requires treatment with another therapeutic agent that is intended for the treatment of psychosis, discontinuation from the study occurs prior to introduction of the new agent
- patient decision
 - o the patient and/or caretaker requests patient withdrawal
- sponsor decision

If a patient discontinues the study early, the site will make every reasonable effort to have the patient return for an early termination visit to have end-of-study procedures performed as shown in the Schedule of Activities (Section 2). If the patient does not return, this will not be considered a protocol deviation.

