10.2. Populations for Analyses

For the purposes of analysis, the following populations are defined:

Population	Description
Randomized	All patients who sign informed consent and are randomized.
Safety	All randomized patients who take at least 1 dose of double-blind study treatment. In the event of a treatment error, patients will be analyzed according to the treatment they actually received.
Intent-to-Treat	All randomized patients who take at least 1 dose of double-blind study treatment and have at least 1 postbaseline efficacy assessment. In the event of a treatment error, patients will be analyzed according to the treatment to which they were randomized.
Evaluable	All patients in the Intent-to-Treat population who complete at least Visit 5 (Week 4) with NPI efficacy data. Specifically, patients with a diagnosis of psychosis must have at least one psychosis sub-scale score at Visit 5 or later and patients with a diagnosis of agitation/aggression must have at least one agitation/aggression sub-scale score at Visit 5 or later.

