## **1.4.** Sample Size Determination

Approximately 100 patients will be enrolled to enable approximately 80 evaluable patients to complete the study through at least Visit 5 (Week 4).

The primary analysis will use a one-sided Fisher's exact test with a 5% type 1 error rate.

If the NPI response rate in MP-101 treated patients is 30% greater than in placebo treated patients (65% vs 35%), with 40 evaluable patients per treatment group there is at least an 80% chance (i.e. Power) that MP-101 will demonstrate superiority to placebo.

The sample size was calculated assuming an expected 20% drop-out rate of patients in each arm prior to Week 4, so that 100 patients are planned to be enrolled to arrive at 40 patients/arm (N=80) in the Evaluable population.

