#### **NPI Response**

Patients whose response to treatment cannot be determined due to missing data (including early withdrawal) will be considered non-responders.

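### The protocol gives two dispositions for a patient who needs rescue, and no SAP rule stops an improvement on rescue from counting as a primary response

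*Protocol*

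**What the plan says.** **Disposition.** Protocol 7.7 (Concomitant Therapy): "Patients with worsening psychosis or agitation/aggression requiring rescue therapy will be withdrawn from the study". Protocol 8.1.1, under discontinuation from study treatment, lists "the occurrence of worsening psychosis and/or agitation or aggression requiring rescue therapy" among the circumstances for stopping investigational product. It continues: "For patients who discontinue the investigational product early, sites will make every reasonable effort to ensure that patients have procedures performed", with reference to the Schedule of Activities. Protocol 8.2, on leaving the study, deals with a patient who needs another agent intended for psychosis: "discontinuation from the study occurs prior to introduction of the new agent". That item stands in a list of circumstances in which patients may be discontinued, and it does not mention agitation/aggression. A patient who leaves under 8.2 is asked to attend one early termination visit.

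**Analysis.** The primary analysis is NPI response at the end of treatment in the Evaluable population (protocol Synopsis and 10.3.3.1). That population consists of Intent-to-Treat patients "who complete at least Visit 5 (Week 4) with NPI efficacy data" (protocol 10.2). SAP 2.7 says: "Patients whose response to treatment cannot be determined due to missing data (including early withdrawal) will be considered non-responders". The only collected data that the SAP excludes are those obtained after unblinding (SAP 2.2). SAP 5.2 maps early termination NPI to the next visit, but only for the mixed models. Neither document says how NPI scores obtained after rescue count towards response.

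**The concern.** Needing rescue for worsening psychosis or agitation is a failure on the symptoms that the primary endpoint measures. How that failure enters the primary comparison should not depend on which section of the protocol a site follows.

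There are two gaps. First, SAP 2.7 turns a patient into a non-responder only when response cannot be determined. A patient who stops study drug, starts rescue and attends Week 10 has an observed NPI, and a 30% improvement achieved on the rescue drug would be credited to the assigned arm. Second, a patient withdrawn before any Visit 5 NPI is not counted as a failure but leaves the primary denominator. Protocol 10.3.1 assumes that early withdrawal is not influenced by the treatment effect, whereas withdrawal for worsening is related to outcome.

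The direction of bias depends on which arm is rescued more. More rescue on placebo works against MP-101, and more rescue on MP-101 works in its favour. The second case matters because it raises the false-positive rate.

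**Working it through.** **Step 1. What happens to a rescued patient**

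| Route | Text that governs | Primary endpoint |
|---|---|---|
| Withdrawn after a Visit 5 NPI | 7.7, SAP 2.7 | Non-responder, in the denominator (use of an early termination NPI is not stated) |
| Drug stopped, visits continued to Week 10 | 8.1.1 reading | Observed NPI counts, so the patient can be a responder |
| Withdrawn before any Visit 5 NPI | 7.7, Evaluable definition | Not in the denominator |

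**Step 2. Reproduce the plan's power.** Inputs from SAP 1.4: 65% v 35%, 40 evaluable per arm, and "The primary analysis will use a one-sided Fisher's exact test with a 5% type 1 error rate". Exact power is the sum, over all pairs (x, y) that the one-sided Fisher test rejects at 0.05, of Bin(x; 40, 0.65) × Bin(y; 40, 0.35). The result is 79.5%, against the stated figure of at least 80%. With equal true rates of 35%, the exact size is 2.9%.

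**Step 3. Rescued patients scored as observed.** Let r be the share of an arm that is rescued (all taken to be failures otherwise), f the share of those followed to Week 10, and q the chance of a 30% improvement on rescue. Those not followed are taken as withdrawn after Visit 5. The observed rate is p + r × f × q. The documents give no value for r, f or q, so all are assumptions; q = 0.5 here.

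| Rescued, MP-101 / placebo | f | MP-101 rate | Placebo rate | Power |
|---|---|---|---|---|
| 5% / 15% | 1 | 0.65 + 0.025 = 67.5% | 0.35 + 0.075 = 42.5% | 64.1% |
| 5% / 10% | 1 | 67.5% | 0.35 + 0.05 = 40.0% | 72.3% |
| 5% / 15% | 0.2 | 0.65 + 0.005 = 65.5% | 0.35 + 0.015 = 36.5% | 76.7% |
| 10% / 10% | 1 | 0.65 + 0.05 = 70.0% | 40.0% | 79.8% |

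For 5% / 15% with all followed, varying q from 0.35 to 0.65 gives power from 69% down to 59%.

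**Step 4. Rescued patients dropped before Visit 5.** With 5% / 15% lost from 40 per arm, the rates are 0.65/0.95 = 68.4% of 38 and 0.35/0.85 = 41.2% of 34. The difference is about 27 points and power is 66.7%.

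**Step 5. More rescue on MP-101.** Take a 35% underlying response in both arms, with 20% of MP-101 and 5% of placebo rescued. If all are followed, q from 0.35 to 0.65 gives rates from 42.0% v 36.75% to 48.0% v 38.25%, and type I error from 7.6% to 15.1%. If all are dropped, the rates are 0.35/0.80 = 43.75% of 32 and 0.35/0.95 = 36.8% of 38, and type I error is 9.1%.

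**Step 6. Sensitivity to one patient.** 22/40 v 14/40 gives p = 0.058. One MP-101 failure rescored as a responder (23/40) gives 0.036. One MP-101 failure dropped (22/39) gives 0.046.

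**The case against.** A reader might infer that 8.1.1 keeps rescued patients in the study with drug stopped. It does not say so. Leaving the study also means stopping drug, neighbouring items in the same list concern events that preclude continuing in the study, and the Schedule of Activities has an early termination column that includes the NPI. So 8.1.1 can be read consistently with 7.7. Against that, the rescue item carries no wording about leaving the study, and 8.1.1 and 8.2 have separate follow-up paragraphs. The text therefore admits both readings.

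A reader might also infer that the rules always either credit rescue to the assigned arm or delete the failure. They do not. Under the plain text of 7.7, a patient withdrawn after Visit 5 is a non-responder by SAP 2.7. For psychosis agents, 8.2 would also close the responder route if followed, but it leaves out agitation/aggression.

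Nor does the disagreement between sections cause the loss from the denominator. That follows from 7.7 together with the Evaluable definition and would remain after reconciliation. The SAP plans for 20% drop-out before Week 4, which covers the numbers but not bias from outcome-related loss. Protocol 10.3.1 says only that analyses of early withdrawal may be done, and the supporting analysis in SAP 5.1 is a stratified test that does not address rescue.

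The objection to the size of the effect also stands in part. The 64% figure needs every rescued patient to be followed despite 7.7. The figures in Step 4 may count early losses twice, because SAP 1.4 applies 65% v 35% to patients who have already reached Week 4.

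**Conclusion.** The concern holds in a limited form. Sections 7.7 and 8.1.1 can be read as giving different dispositions for the same event, 8.2 settles it only for psychosis agents, and no analysis rule covers NPI scores obtained after rescue. The route by which a rescued patient becomes a responder is open only if patients are followed under the 8.1.1 reading. The exclusion of patients rescued and withdrawn before Visit 5 is a separate consequence of the analysis set.

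The size is unknown because the documents give no rescue rates. On the assumed rates, power ranges from about unchanged (equal 10% rescue) through about 77% (5% v 15%, one in five followed) to 64% (all followed), against 79.5% by design. The 64% is an adverse case and not an expected value. If MP-101 patients are rescued more, the bias favours the drug. In a trial of 40 per arm, one reclassified patient can move the result across the 5% line.

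**What to change.** 1. Reconcile protocol 7.7, 8.1.1 and 8.2 on the disposition of a patient who needs rescue, covering agitation/aggression as well as psychosis. No view is taken here on which clinical rule is right.
2. In SAP 2.7, before unblinding, state that an Evaluable patient discontinued for rescue therapy, or starting it, is a non-responder on NPI response and Core Total response, whatever later or early termination NPI scores exist.
3. Flag post-rescue NPI values in the mixed models of SAP 5.2.
4. Add a sensitivity analysis of the primary response that keeps patients rescued before Visit 5 in the denominator as non-responders. It fits better there than in the primary analysis, where restoring rescue cases but not other early losses would redefine Evaluable selectively and change the basis of the sample size.
5. Confirm that the eCRF discontinuation reason and the concomitant medication records identify rescue. Neither document defines rescue therapy or shows a field for it, and an agent started after study exit may not be recorded.

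The cost is a protocol clarification, a few sentences in the SAP, one extra analysis and a check of the eCRF. Response rates may be slightly lower. If all rescued patients are counted as failures at the planned 65% v 35%, power stays at 79.5%.
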